##### **9.1.4.1 Visit 6 (Day 31)**

Visit 6 will occur 30 days after the first dose of IMP. A visit window of  $\pm 1$  day from the scheduled visit date is permitted, but it is preferred that the visit is performed on the scheduled visit day, where possible.

The following assessments/procedures will be performed on Day 31 predose:

- Concomitant medications review
- AE review
- Examination of oral mucosa
- Body weight measurement
- Vital signs measurement
- Urine pregnancy test (if appropriate)
- PK blood sampling for IMP ([Section 9.2.12.1](#))
- MAS assessment
- T25FW test
- C-SSRS assessment
- IMP dispensing

Following predose assessments and IMP dispensing, patients will administer a single dose of IMP with a standardized snack containing at least 300 kcal (of which approximately 30 kcal is composed of fat) at the trial site under the supervision of site staff.

The following assessments/procedures will be performed 2 to 4 hours postdose:

- MAS assessment (3 hours  $\pm 15$  minutes postdose)
- AE review
- Vital signs measurement

- PK blood sampling for IMP ([Section 9.2.12.1](#))

The patient will be provided dosing instructions and advised to contact the investigational site when in doubt about changes in the daily dose of IMP. The patient will be instructed to record IMP doses administered in the patient electronic diary.

The exact time of PK blood sampling and the time of the patient's snacks and meals should be recorded.

Following Visit 6, patients will titrate their daily dose of IMP for approximately 14 days until they achieve an optimized dose with an approximately 15-minute interval between sprays; patients should divide doses greater than 1 spray/day into a morning dose and an evening dose. Administration of the morning and evening doses of IMP should be maintained around the same time each day in a consistent manner in relation to food consumption, i.e., within 30 minutes after starting a snack or meal.

Patients should be reminded to record their 11-point NRS spasticity score, spasm count, and use of antispasticity medications in the electronic diary once daily, around the same time each day, preferably in the evening before retiring to sleep. In addition, on the day before Visits 8 and 9, patients will be prompted to record whether they started their morning and evening doses of IMP within 30 minutes of a snack or meal.

Each site will have the option to follow-up with the patient through telephone calls during the titration phase to monitor the patient's titration, safety and tolerance, and electronic daily diary reporting.

#### **9.1.4.2 Visit 7 (Day 38, Phone Call)**

Visit 7 will occur 7 days after the first dose of IMP during Period 2 and will consist of a phone call from site staff to patients to monitor adherence with IMP administration and advise on dose titration if required. Concomitant medications and AEs will be collected during this call.

#### **9.1.4.3 Visit 8 (Day 45) and Visit 9 (Day 51, End of Treatment)**

Visits 8 and 9 will occur 44 and 50 days after the first dose of IMP, respectively. A visit window of  $\pm 1$  and  $\pm 2$  days, respectively, from the scheduled visit date is permitted, but it is preferred that the visit is performed on the scheduled visit day, where possible.

Once a stable daily dose has been reached, patients should gradually decrease the interval between sprays to a target interval of approximately 1 minute between sprays. Patients should continue IMP administration at the same dose level achieved at the end of titration (i.e., their daily optimized dose)  $\pm 1$  spray divided into a morning dose and an evening dose for approximately 7 days (maintenance-dose phase). Administration of the morning and evening

doses of IMP should be maintained around the same time of each day in a consistent manner in relation to food consumption, i.e., within 30 minutes after starting a snack or meal.

On Visit 9, patients will administer the morning dose of IMP with a standardized snack containing at least 300 kcal (of which approximately 30 kcal is composed of fat) at the trial site under the supervision of site staff. The IMP will not be administered in the evening of Visit 9 (Day 51).

The following assessments/procedures will be performed at these visits, unless otherwise indicated:

- MAS assessment (Visit 9 [3 hours  $\pm$ 15 minutes after the first spray of the morning dose] only)
- T25FW test (Visit 9 only)
- Concomitant medication review
- AE review
- Physical examination (Visit 9 only)
- Examination of the oral mucosa
- Vital signs measurement
- 12-lead ECG (Visit 9 only)
- Clinical laboratory sampling (hematology and biochemistry) (Visit 9 only)
- PK blood sampling for IMP ([Section 9.2.12.1](#))
- MSSS-88 assessment (Visit 9 only)
- C-SSRS assessment
- IMP dosing at the investigational site (Visit 9 [morning] only)
- IMP dispensing (Visit 8 only)
- IMP collection and compliance review

The exact time of PK blood sampling and the time of the patient's snacks and meals should be recorded.

Patients should be reminded to record their 11-point NRS spasticity score, spasm count, use of antispasticity medications, and IMP dosing in the electronic diary once daily, around the same time each day, preferably in the evening before retiring to sleep.

If the decision is made to discontinue IMP early, the patient concerned will be encouraged to remain in the study for the duration of the treatment period in which they discontinue IMP and will complete an End of Treatment Visit (Visit 9) at the end of that period.

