## **Definition of Terms**

Term	Definition
Clonus	A clinical manifestation of spasticity described as self-sustained rhythmic involuntary muscular contractions and relaxations in response to a muscle stretch
Completer	A patient who completes both treatment periods
Day 1	The day a patient first receives investigational medicinal product in this trial
End of trial	Last patient last visit or last contact, whichever occurs last
Enrolled patient	Any patient who has provided written informed consent to take part in the trial
International normalized ratio	A calculation made to standardize prothrombin time
Investigational medicinal product	Term used to describe both investigational active product and reference therapy (placebo)
Investigator	Trial principal investigator or a formally delegated trial physician
Lower Limb Muscle Tone-4	A measure of velocity-dependent muscle tone in the lower limbs consisting of the average of the 4 individual MAS transformed scores of knee flexors and knee extensors on both sides of the body
Lower Limb Muscle Tone-6	A measure of velocity-dependent muscle tone in the lower limbs consisting of the average of the 6 individual MAS transformed scores of knee flexors, knee extensors, and plantar flexors on both sides of the body
Spasm	A clinical manifestation of spasticity described as a sudden, involuntary contraction of a muscle
Spasticity	A velocity-dependent increase in muscle tone resulting from an upper motor neuron lesion. Clinically, spasticity manifests as muscle stiffness or tightness, increased tendon reflexes, clonus, and flexor and extensor spasms
Standardized snack	A meal containing at least 300 kcal (of which approximately 30 kcal is composed of fat)

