## Appendix 1 SCHEDULE OF ASSESSMENTS

Period	Screening		Treatment Period 1				Treatment Period 2				Safety Follow-up
	Visit 1	Visit 2	Visit 3 (Phone C all)	Visit 4	Visit 5 a	Visit 6	Visit 7 (Phone Call)	Visit 8	Visit 9		
Day/Hour	Days-28 to -1	Day 1 predose	Day 1 2-4 hrs postdose	Day 8 (±1 day)	Day 15 (±1 day)	Day 21 (±2 days)	Day 31 predose (±1 day)	Day 31 2-4 hrs postdose	Day 38 (±1 day)	Day 45 (±1 day)	Day 51 (±2 days) End of Treatment Visit
Informed consent	X										Day 58 (+ 3 days)
Eligibility check	X	X									
Demographics	X										
Previous cannabis use	X										
Medical history	X										
Electronic diary training	X										
Randomization		X									
Concomitant medications											Assessed at each visit
AEs											Assessed at each visit
Physical examination b	X					X					X
Examination of oral mucosa	X	X			X	X	X			X	X
Body weight measurement	X	X					X				X
Vital signs	X	X	X		X	X	X			X	X
12-lead ECG	X					X					X

Period	Screening		Treatment Period 1				Treatment Period 2			Safety Follow-up
	Visit Number	Visit 1	Visit 2	Visit 3 (Phone C all)	Visit 4	Visit 5 a	Visit 6	Visit 7 (Phone Call)	Visit 8	
Day/Hour	Day -28 to -1	Day 1 predose	Day 1 2-4 hrs postdose	Day 8 ( $\pm 1$ day)	Day 15 ( $\pm 1$ day)	Day 21 ( $\pm 2$ days)	Day 31 predose ( $\pm 1$ day)	Day 38 ( $\pm 1$ day)	Day 45 ( $\pm 1$ day)	Day 51 ( $\pm 2$ days) End of Treatment Visit
Clinical laboratory blood sampling (hematology and biochemistry)	X									
Dipstick urinalysis	X					X				
Urine drug screen (including THC)	X	X								
Serum/urine pregnancy test (if appropriate) c	X	X					X			
Blood THC test	X									
PK blood sampling (IMP) d		X	X			X	X	X	X	
11-Point NRS spasticity e	X	X				X	X			
Daily spasm count e	X	X				X	X			
Use of antispasticity medications e	X	X				X	X			
IMP dosing record e		X				X	X			

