10.1.2 Reference Day and Study Day

The reference day (Day 1) will be the day of the first dose of study drug administration.

For a patient who was randomized but not exposed, the reference day date will be imputed by the randomization date.

The reference day for Period 1 (Period 1 Day 1) will be the reference day.

The reference day for Period 2 (Period 2 Day 1) will be the first day of IMP administration during Period 2. For a patient who entered the second period but was not exposed during this period, this reference day date will be imputed by the date of Visit 6 IRT call, if any, or the Visit 6 date.

The study day is defined relative to the reference day date. For assessments that occur after this visit date, the study day is calculated as (assessment date – reference day date + 1). For assessments that occur prior to first dose date, study day will be calculated as (assessment date – reference day date).

For the analyses being done by treatment arm, an **analysis day** will need to be derived for each treatment period as described in Table 10.1-1. The analysis day is defined relative to the date of reference day of each study period.

For assessments that occur prior to reference day date, analysis day will be calculated as (assessment date – reference day date);

For assessments that occur on or after the Period 1 reference day date until the end of the wash-out period, analysis day will be calculated as (assessment date – Period 1 reference day date +1);

For assessments that occur on or after Period 2 reference day date the analysis day will be calculated as (assessment date – Period 2 reference day date +1);

Thus, there is no study day or analysis day referring to Day 0.

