	Visit 5 / Day 21	Day 21***		Day 19 up to LP1V	Day 19 up to LP1V	Day 1 post dose of 1 st IMP intake up to LP1V	Day 1 post dose of 1 st IMP intake up to LP1V
Wash out period							
Period 2	Visit 6 / Day 31	Day 1H0*		Day 1 – 4 days to D1H0 *	Day 1H0 (before P2 IMP intake)	Day 1H0 (before P2 IMP intake)	Day 1H0 (before P2 IMP intake)
	Visit 6 / Day 31	Day 1H2- H4**			Day 1 post dose (the day of 1 st P2 IMP intake)** up to Day 18		
	Visit 8 / Day 45	Day 15		Day 2 (day following IMP intake) – Day 18 (or the first day of maintenance phase)			
	Visit 9 / Day 51	Day 21***		Day 19 to LP2V	Day 19 to LP2V	Day 1 post dose of Period 2 1 st IMP intake up to LP2V	Day 1 post dose of Period 2 1 st IMP intake up to LP2V
Follow-up	Visit 10 / Day 58	Day 28****		After last IMP dosing			

H = Hours, P = Period; LP1V = Last visit during Period 1, LP2V = Last visit during Period 2, IMP = Investigational Medicinal Product, NRS = Numerical Rating Scale; IRT = Interactive Response System, MAS = Modified Ashworth Scale, MSSS-88 = Multiple Sclerosis Spasticity Scale; T25FW = Timed 25-Foot Walk.

* Day 1 is based on the date of IRT call within each period.

** D1H2-H4 for sensitivity analysis purpose only assessments collected between at H3 (+/- 15 min) post first IMP morning spray will be considered. Should be collected during the titration phase

*** Day 21 should be collected during the maintenance phase (including off-treatment days).
 **** Day 28 relative to the period where IMP is permanently discontinued.

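### Period 2 visits are timed from the first trial dose but windowed from the first Period 2 dose, so one permitted visit pair puts a compliant Visit 9 MAS outside the Day 21 window

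*Protocol*

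**What the plan says.** **Protocol.** Day 1 is defined once for the whole trial: "The day a patient first receives investigational medicinal product in this trial" (Definition of Terms). Section 9.1.4.1 states "Visit 6 will occur 30 days after the first dose of IMP", with a window of ±1 day. Section 9.1.4.3 states "Visits 8 and 9 will occur 44 and 50 days after the first dose of IMP, respectively", with ±2 days for Visit 9; Appendix 1 agrees ("Day 51 (±2 days) End of Treatment Visit"). Only the telephone call between them has a different origin: "Visit 7 will occur 7 days after the first dose of IMP during Period 2" (9.1.4.2).

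**SAP.** Section 10.1.2 makes the first Period 2 dose the Period 2 reference day: "For assessments that occur on or after Period 2 reference day date the analysis day will be calculated as" assessment date minus that date plus 1. A footnote to Table 10.1-3 bases Day 1 on the Period 2 IRT call, normally the same day. In Table 10.1-3 the Period 2 Day 21 MAS window runs from Day 19 to the last Period 2 visit. The Day 1 post-dose (H3) MAS window is "Day 1 post dose (the day of 1 st P2 IMP intake) up to Day 18" (a footnote marker in the cell is left out here). Where several values share a window, 10.1.3 keeps the one closest to the target day.

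Three other SAP statements bear on this. Table 10.1-1 pairs Visit 9 with analysis visit Day 21. The footnotes to Table 10.1-3 expect Day 21 values from the maintenance phase and Day 1 H3 values from titration. Section 10.8.1 starts Period 2 maintenance on the date of Visit 8.

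**The concern.** Visits 6 and 9 each have their own tolerance around a fixed trial day, so the interval between them can vary by the sum of the two tolerances. The SAP window allows for only one of them. A late Visit 6 followed by an early Visit 9 therefore gives a patient who has met every visit window but whose final MAS the analysis does not recognise as the endpoint.

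At stake are that patient's Period 2 LLMT-6 and LLMT-4, and with them the within-patient contrast. Under the June 2022 SAP an observed value would be replaced by an imputed one (Table 12.5-1). Under the addendum LLMT-6 is analysed without imputation, so the value would simply be absent.

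The result looks unintended. In the same table the Period 2 windows for T25FW and MSSS-88 run from post-dose Day 1 to the last Period 2 visit, so the same Visit 9 would keep its exploratory endpoints and lose its primary one. No MAS is scheduled between Day 1 and Visit 9, so running the Day 1 H3 window to Day 18 serves no planned assessment.

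**Working it through.** **Inputs.** Visit 6: 30 days after first dose, ±1 (Protocol 9.1.4.1). Visit 9: 50 days after first dose, ±2 (9.1.4.3). Analysis-day formula: SAP 10.1.2. Window bounds: SAP Table 10.1-3.

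**Nominal schedule.** Trial day = days after first dose + 1, so Visit 6 is 30 + 1 = Day 31 and Visit 9 is 50 + 1 = Day 51. Period 2 analysis day = 51 − 31 + 1 = 21. The schedule and the SAP agree when both visits are on time.

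**All permitted pairs.** Period 2 analysis day = Visit 9 day − Visit 6 day + 1:

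| Visit 6 | Visit 9 on Day 49 | 50 | 51 | 52 | 53 |
|---|---|---|---|---|---|
| Day 30 | 20 | 21 | 22 | 23 | 24 |
| Day 31 | 19 | 20 | 21 | 22 | 23 |
| Day 32 | **18** | 19 | 20 | 21 | 22 |

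The range is 18 to 24. Only 49 − 32 + 1 = 18 falls below the bound of 19: 1 pair in 15. In Period 1, Visit 5 at Day 21 ±2 gives Days 19 to 23, all inside the window.

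**Where the Day 18 value goes.** By its day number it belongs to the Day 1 H3 window. The Visit 6 three-hour MAS, taken on Day 1 itself, is closer to target and is kept. If that value is missing, the Day 18 MAS could be used as Day 1 H3. By phase it belongs to Day 21: with Visit 6 on Day 32, Visit 8 (trial Days 44 to 46) is Period 2 Day 13, 14 or 15, so maintenance has begun before Day 18. I found no rule that gives the nominal visit or the phase precedence over the day bound.

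**How often.** The documents give no visit-date distribution, so these are assumptions with the two visits independent:
- P(Visit 6 one day late) = 0.10 and P(Visit 9 two days early) = 0.05: 0.10 × 0.05 = 0.5%; 170 × 0.005 = 0.85 patients.
- 0.25 and 0.10: 0.25 × 0.10 = 2.5%; 170 × 0.025 = 4.25 patients.

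**Effect on power.** With a difference of 0.18, paired SD 0.71 and two-sided 5%, a paired t-test needs 166 completers for 90% power, consistent with the planned 170, which gives 90.8%. Losing 1, 2 or 5 whole pairs gives 90.6%, 90.4% or 89.9%. These figures overstate the loss slightly, because the mixed model still uses the patient's Period 1 change.

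**By-visit safety summaries.** In Table 10.1-2 the Day 21 windows for C-SSRS, oral mucosa and vital signs also start at Day 19. A Day 18 record shares the Day 15 window with Visit 8. It is 18 − 15 = 3 days from target, against 0 to 2 for Visit 8, so it drops out of the by-visit table.

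**The case against.** The best reply is that the SAP can be read so that nothing is lost. Table 10.1-1 ties Visit 9 to Day 21, and the phase footnotes fit a Visit 9 MAS to Day 21 and not to Day 1 H3. This stands to the extent that the SAP contradicts itself rather than clearly ordering the loss. But the day bound is the explicit numerical rule that would be programmed, and the footnotes describe when values should be collected without saying that they override it.

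A second reply is that Day 19 is a coherent bound: it is Day 21 minus the two-day tolerance, and the estimand refers to 21 days of the period. That holds in Period 1. In Period 2 the protocol permits an interval one day shorter. Whether an 18-day value should count as Day 21 is partly a choice, but it should be made openly.

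Third, the problem is rare and has no evident direction. It depends on visit dates and can arise in Period 2 of either sequence. This stands. A reader might infer from 1 pair in 15 that 6.7% of patients, about 11 of 170, would lose the endpoint. That needs visits spread evenly over their windows, whereas the protocol prefers the scheduled day at both visits, and it needs a full sample, whereas the addendum says enrolment stopped short of plan.

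A reader might also infer a wider loss of safety data. The SAP does not support that: C-SSRS is also summarised over the on-treatment period and at the last and worst on-treatment assessments, vital-sign abnormalities are counted over the whole period, and the ECG and laboratory windows start after dosing on Day 1.

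**Conclusion.** The inconsistency between protocol and SAP is real and follows from their own day counts. It affects exactly one permitted combination, Visit 6 on Day 32 with Visit 9 on Day 49, and only in Period 2. If the day bound is applied as written, that patient's observed LLMT-6 and LLMT-4 are treated as missing under the June 2022 SAP; for LLMT-6 under the addendum there is no imputation either.

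The size is small: about 1 to 4 of the planned 170 under the assumed rates, fewer and possibly none after early termination, with a power cost under about 1 percentage point. No bias is shown. The point is worth correcting because it concerns observed primary-endpoint data and costs almost nothing to settle, not because it threatens the trial's conclusion.

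**What to change.** - **SAP Table 10.1-3:** state that the MAS collected at Visit 9 within its protocol window is analysed as Period 2 Day 21, and end the Day 1 H3 MAS window on the dosing day.
- **SAP Table 10.1-2:** apply the same nominal-visit rule to C-SSRS, oral mucosa and vital signs. Moving the Day 21 start to Day 18 would overlap the Day 15 rows, which end on Day 18.
- **Protocol 9.1.4.1 to 9.1.4.3 and Appendix 1:** reconcile the Period 2 visits on one anchor if the protocol is otherwise being amended. The point does not justify an amendment by itself.

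The cost is a short rule and a few cell edits across two SAP tables, made before unblinding, with no new data or patients. The downside is that a few values taken on Period 2 Day 18 are kept as Day 21.

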### **9.1.5 Safety Follow-up Visit (Visit 10 [Day 58])**

The Safety Follow-up Visit will occur 7 days after the last dose of IMP or after the End of Treatment visit (Visit 9), whichever is later. A visit window of + 3 days from the

scheduled visit date is permitted, but it is preferred that the visit is performed on the scheduled visit day, where possible.

The following assessments/procedures will be performed:

- Concomitant medication review
- AE review
- Examination of oral mucosa
- Body weight measurement
- Vital signs measurement
- Dipstick urinalysis
- Serum pregnancy test (if appropriate)
- C-SSRS assessment

## **9.2 Trial Procedure Listing**

### **9.2.1 Informed Consent**

Adult patients with an adequate level of understanding must personally sign and date the IRB/IEC-approved ICF before any trial-specific procedures are performed or any patient-related data are recorded for the trial. If an adult patient is unable to read (illiterate or visually impaired), or is physically unable to speak or write, an impartial witness should be present during the entire informed consent discussion. After the ICF is read and explained to the patient and after the patient has orally consented to participation in the trial and has signed and dated the ICF (if capable of doing so), the witness should also sign and personally date the ICF. By signing the ICF, the witness attests that the information in the ICF was accurately explained to and apparently understood by the patient and that informed consent was freely given by the patient (as outlined in the International Council for Harmonisation [ICH] Tripartite Guideline for Good Clinical Practice [GCP] Topic E6(R2), Section 4.8.9).

If the patient cannot write, they can give consent by “making their mark” on the consent form (e.g., writing an “X”).

The original signed ICF should be retained, and a copy should be provided to the patient. For further details regarding the informed consent, see [Section 15.2](#).

### **9.2.2 Contraception Requirements**

To be eligible for the trial, female patients of childbearing potential (i.e., following menarche and until becoming postmenopausal for  $\geq 12$  consecutive months unless permanently sterile by hysterectomy, bilateral salpingectomy, or bilateral oophorectomy) must have agreed that they are willing to use highly effective contraception for the duration of the trial and for 3 months thereafter. Highly effective methods of birth control are defined as those, alone or in combination, that result in a low failure rate (i.e., less than 1% per year) when used

consistently and correctly. Such methods include an intrauterine device/hormone-releasing system, bilateral tubal occlusion, vasectomized partner (provided that partner is the sole sexual partner of the trial patient and that the vasectomized partner has received medical assessment of the surgical success), or sexual abstinence. Due to the possible interaction of the IMP with contraceptive steroids, the use of hormonal contraception must be supplemented with a barrier method (preferably male condom or diaphragm).

To be eligible for the trial, male patients who are fertile (i.e., after puberty unless permanently sterile by bilateral orchectomy) must have agreed that they are willing to use male contraception (condom or vasectomy) or remain sexually abstinent during the trial and for 3 months thereafter.

Abstinence, as referenced above, is only acceptable as true abstinence, i.e., when this is in line with the preferred and usual lifestyle of the patient. Periodic abstinence (calendar, symptothermal, and postovulation methods), withdrawal (coitus interruptus), spermicides only, and the lactational amenorrhea method are not acceptable methods of contraception.

